#### 4.9.1.3. Responders

Responders are defined as patients who have  $\geq 50\%$  decrease in the WOMAC A score from baseline at a given visit. Descriptive statistics (number of evaluable patients and number and percent with  $\geq 50\%$  response) will be presented for Weeks 4 through 52 by the following groups. Each group will be displayed as a different column in the same table, in this order:

1. Patients receiving the second dose at Week 12
2. Patients receiving the second dose at Week 16
3. Patients receiving the second dose at Week 20
4. Patients receiving the second dose at Week 24
5. Patients receiving only one dose
6. All patients, first dose – all patients through patient discontinuation, study completion (through Week 12 or Week 24), or until the second dose is received (whichever happens sooner)

Response rate will be plotted by group with a bar chart.

Additionally, for Week 12, a continuous responder curve will display the cumulative proportion of responders on the y-axis versus the criteria/cut point used to define a responder on the x-axis;

in this figure, lines will display the proportion of patients responding under various % improvement cut points by group. Each group will be plotted on a separate line. Jitter will be used as needed to distinguish overlapping data.

#### 4.9.1.4. Area Under the Effect Curve (AUE) for Change from Baseline in WOMAC over Time

The Area Under the Effect curve (AUE) for change from baseline in WOMAC A, B, C and total score over various time intervals will be examined.

AUE will be calculated from a linear trapezoidal rule using the following formula for change from baseline in WOMAC A, WOMAC B, WOMAC C and WOMAC total:

$$AUE_{t_i-t_{i+n}} = \sum_{t_i}^{t_{i+n}} ((WD_i + WD_{i+1})/2) * (t_{i+1} - t_i)$$

Where  $WD_i$  = WOMAC difference (change) from baseline in WOMAC score for time  $t_i$ , and  $WD_{i+1}$  = WOMAC difference (change) from baseline in WOMAC score for time  $t_{i+1}$ , over the time interval  $t_i$  to  $t_{i+1}$ . (Note that the difference for  $t_{i+1} - t_i$  will be 4 week intervals). Only non-missing time intervals will be part of the sum for each AUE calculation (Farrar et al. 2000). Baseline for the first dose will be used for all WOMAC difference from baseline calculations.

Two within patient analyses will be completed for patients who receive two doses of FX006. In the first analysis, the AUE for the change from baseline for the first dose from Week 4 to Week 12 will be compared to the AUE for the change from baseline for the second dose from 4 to 12 weeks after the second dose for all patients. In the second analysis, the AUE for the change from baseline for the first dose from Week 4 to the second dose will be compared to the AUE for the change from baseline for the second dose from 4 weeks after the second dose to the comparable period after the second dose.

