## 7. INVESTIGATIONAL PLAN

### 7.1. Overall Study Design and Plan

This study is an open-label, repeat administration design of 32 mg FX006. The study will be conducted in male and female patients  $\geq$  40 years of age with symptomatic OA of the knee.

Eligible patients will be offered participation to receive an initial IA injection of FX006 administered to the index knee at Day 1

Patients who receive an initial injection of FX006 will return at Weeks 4 and 8 before being evaluated at 12, 16, 20, and 24 weeks following the initial administration of FX006 for repeat administration. At the first visit where the patient has been determined to meet repeat administration eligibility criteria described in Section 7.4.3, the patient will be eligible to receive a second IA injection of FX006 administered to the index knee.

Patients who are eligible to receive a second injection will be evaluated for a total of 52 weeks post initial injection at: Weeks 4, 8, 12, 16, 20, 24, 28, 32, 36, 40, 44, 48, and 52, regardless of the visit at which they receive their second injection.

Patients that do not benefit from the initial treatment as determined by evaluation at Week 12 will complete the study at the Week 12 follow-up visit. These patients will be evaluated for a total of 12 weeks post initial injection at: Weeks 4, 8, 12.

Patients who are not eligible for a second injection of FX006 after evaluation at Weeks 12, 16, 20, and 24 will complete the study at the Week 24 follow-up visit. These patients will be evaluated for a total of 24 weeks post initial injection at: Weeks 4, 8, 12, 16, 20, and 24.

Refer to [Appendix 2 Study Visit Flow Chart](#).

The study is expected to enroll over approximately 6 months.

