##### **7.4.3.1. Repeat Administration Inclusion Criteria**

To be eligible to receive a repeat administration, patients must fulfill the following criteria:

1. Benefit from the initial dose of FX006 in the opinion of both the patient and the Investigator
2. No major safety concerns during the initial dose period as assessed by the Investigator
3. Clinically indicated to receive a second dose of FX006 in the opinion of both the patient and the Investigator
4. WOMAC A total sum score of  $\geq 6$  or a clinical rationale as to why a second dose is indicated
5. Compliant with study procedures and visit schedules through at least Week 12 and the willingness and ability to continue to comply through Week 52
6. Willingness to abstain from use of protocol-restricted medications during the study

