The paired t-test will be completed by using the SAS/STAT® PROC MIXED procedure. Model covariates are study site, baseline WOMAC score, and potentially other covariates. Baseline WOMAC score for the first dose comes from the baseline visit. Baseline WOMAC score for the second dose comes from the second dose visit. Sample SAS code provided in section 4.9.1.2 will be used.

Descriptive statistics will include the LSM and standard error, 95% confidence interval, LSM difference from control (first dose to second dose), and 2-sided p-value. This model assumes missing at random and only includes observed data; missing data are not imputed in this model. Only patients that have data for both time points will be included in the model.

Table 3 shows the AUE intervals that will be computed and compared:

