**Table 3 AUE Change from Baseline Comparisons**

AUE	Patients receiving the second dose at Week 12	Patients receiving the second dose at Week 16	Patients receiving the second dose at Week 20	Patients receiving the second dose at Week 24
First Dose	Week 4 to Week 12	Week 4 to Week 16	Week 4 to Week 20	Week 4 to Week 24
Second Dose	Second Dose Week 4 to Week 12 (Week 16 to Week 24)	Second Dose Week 4 to Week 16 (Week 20 to Week 32)	Second Dose Week 4 to Week 20 (Week 24 to Week 40)	Second Dose Week 4 to Week 24 (Week 28 to Week 48)

Both within patient analyses will be presented in the same table. Each group will be displayed as a different column in the same table, in this order:

1. All patients receiving two doses
2. Patients receiving the second dose at Week 12

3. Patients receiving the second dose at Week 16
4. Patients receiving the second dose at Week 20
5. Patients receiving the second dose at Week 24

The analysis above will also be performed where baseline for the second dose is defined as the baseline/Day 1 assessment prior to administration of the first dose of study treatment.

All AUE data will be presented in a data listing. For patients receiving only one dose, the AUE for change from baseline for Week 4 to Week 12 will be presented.

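### In the SAP's AUE comparison, the columns by second-dose timing and the window ending at re-dosing both depend on the patient's own first-dose score; with a Day 1 baseline, equal doses then differ by column

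*SAP*

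**What the plan says.** **When the second dose is given.** Protocol 7.1 (repeated in SAP 2.1) makes a patient eligible for it "At the first visit where the patient has been determined to meet repeat administration eligibility criteria", looking at Weeks 12, 16, 20 and 24. Among the criteria in Protocol 7.4.3.1 are a WOMAC A sum of at least 6 "or a clinical rationale as to why a second dose is indicated", and "Benefit from the initial dose of FX006 in the opinion of both the patient and the Investigator".

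**What is compared.** SAP 4.9.1.4 has two within-patient AUE analyses for two-dose patients.
- Fixed window: Weeks 4-12 after dose 1 against 4-12 weeks after dose 2, all two-dose patients pooled.
- Comparable period: "the AUE for the change from baseline for the first dose from Week 4 to the second dose will be compared" with the same length after dose 2. Table 3 gives the intervals for re-dosing at Weeks 12, 16, 20 and 24.

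**How it is reported.** "Both within patient analyses will be presented in the same table", with one column for all two-dose patients and one per re-dose week. The comparable-period output includes a 95% CI and "LSM difference from control (first dose to second dose), and 2-sided p-value". SAP 4.2.5 makes no multiplicity adjustment. SAP 4.2.1 describes p of 0.05 or below as significant and potentially informative.

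**Which baseline.** The AUE formula text says "Baseline for the first dose will be used for all WOMAC difference from baseline calculations". The model text for both comparisons says "Baseline WOMAC score for the second dose comes from the second dose visit". Each comparison is then to be repeated with Day 1 as the second-dose baseline, which implies that the main version uses the re-dose visit.

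**The concern.** The score that helps to qualify a patient for re-dosing is also the last point of that patient's first-dose AUE. Patients in the Week 16, 20 and 24 columns are there partly because their earlier first-dose scores were low enough not to qualify. No score closes or selects the second-dose window. A paired test within a timing column therefore sets a window selected on the outcome against one that was not. The missing-at-random assumption stated in the SAP does not help, because the scores that drive the selection are observed.

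At stake is the reading of the four columns. If early re-dosing shows a gain and later re-dosing a loss, each with a p-value, this could be taken as a finding about timing when it is partly selection. SAP 4.3 allows interim results on exploratory endpoints to be used for regulatory updates or publication.

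**Working it through.** **No AUE figure to reproduce.** The only sizing figure is 200 x 0.66 x 0.75 = 99, against the stated 100. It has no bearing here. SAP section 5 reports that more than 90% were re-dosed.

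**1. Direction, from the trapezoid rule.** With 4-week steps, the first and last scores in a window carry weight 2 and interior scores weight 4.
- Week 12 column (Weeks 4, 8, 12; weights 2, 4, 2): the Week 12 score is selected high. The first dose looks worse than it is, so dose 2 looks better.
- Week 16 column (weights 2, 4, 4, 2): Week 12 is selected low with weight 4, Week 16 high with weight 2. On balance dose 1 looks better.
- Week 24 column: Weeks 12, 16 and 20 are selected low (total weight 12), Week 24 high (weight 2). The effect is larger.

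**2. Role of the baseline.** For baseline B and window length L, AUE = (area under the score) - B x L. With Day 1 for both doses, B cancels in dose 2 minus dose 1. With the re-dose score B2 for dose 2, (B1 - B2) x L is added.

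**3. Size with equal doses and Day 1 baseline.** The documents give no WOMAC SDs, curve or timing split, so these are assumptions.
- *Model A* (0-4 scale, 200 enrolled): patient SD 0.5, response SD 0.4, visit noise SD 0.4. Mean score 0.95, 0.90, 1.10, 1.30, 1.45, 1.60 at 4 to 24 weeks after either dose. Entry at 6/5 items = 1.2 or more. Re-dosing at 1.2 or more, or with 15% probability for a clinical rationale. 92-94% are re-dosed (57/20/10/6% at Weeks 12/16/20/24).
- *Model B* (0-20 sum, divided by 5 below): patient mean 11, SD 3; mean falls 5.5, 5.5, 5, 4, 3, 2; visit noise SD 2, dose-occasion SD 1; some benefit required by Week 12; score-driven re-dosing. 93.5% are re-dosed.

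Mean AUE2 minus AUE1 in score-weeks on the 0-4 scale, Week 4 to re-dose; negative means dose 2 looks better:

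| | Week 12 | Week 16 | Week 20 | Week 24 | Pooled |
|---|---|---|---|---|---|
| Model A (two runs) | -0.27 | +0.68 to +0.70 | +1.16 to +1.19 | +1.48 to +1.58 | +0.19 to +0.20 |
| A, false significance | 15-25% per column | | | | 13-14% |
| Model B | -2.1/5 = -0.42 | 5.1/5 = +1.02 | 10.4/5 = +2.08 | 16.1/5 = +3.22 | 2.0/5 = +0.40 |
| B, false significance | 26% | 27% | 41% | 43% | 24% |

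Pooled Weeks 4-12: Model A -0.01 to 0.00 (5-6%); Model B 0.2/5 = +0.04 (5%). Across all Model B scenarios it ran from -1.5/5 = -0.30 to 0.6/5 = +0.12, with rejection 5-15%.

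**4. Controls and ranges (Model B).** With no within-patient variation every column is 0.0. With re-dosing unrelated to the score, columns lie between -0.2/5 = -0.04 and 1.2/5 = +0.24 and the sign pattern disappears. With half the decisions unrelated to the score, Week 12 falls to -0.8/5 = -0.16 and Week 24 to about +2. Over the other score-driven scenarios Week 12 ran from -0.16 to -0.98 and Week 24 from +0.90 to +4.14. Model A with clinical-rationale probability 0% or 40% gave the same pattern.

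**5. Size with the re-dose-visit baseline.** Model B, unadjusted, sum-score-weeks, from step 2:
- Week 12: (12.9 - 8.8) x 8 - 2.1 = +30.7
- Week 16: (10.8 - 7.7) x 12 + 5.1 = +42.3
- Week 20: (9.9 - 7.5) x 16 + 10.4 = +48.8
- Week 24: (9.3 - 7.5) x 20 + 16.1 = +52.1

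All go against dose 2. With each dose's own baseline also as covariate they are +11.7, +9.3, +13.0 and +18.4. Model A with that covariate (Day 1 mean assumed 2.0) gives +0.47, +1.58, +2.23 and +2.39 on the 0-4 scale.

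The pooled Weeks 4-12 test is also affected in Model A: +5.1 unadjusted; +0.66 with the covariate (about 51% false significance); -0.42 (about 31%) with Day 1 differences and the re-dose score as covariate.

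**The case against.** - **The test simulated in step 3 is a paired t-test, not the SAP's mixed model.** With Day 1 baseline throughout, baseline and site are constant within a patient. In complete pairs the random-intercept model then gives the same dose contrast. The objection stands for the versions that use the re-dose score, which is why step 5 treats them separately.
- **Opposite signs are not general.** This stands. A reader might infer that early re-dosing always appears favourable and late re-dosing unfavourable. The documents do not support that, because under the re-dose-visit baseline all columns move against dose 2, mainly through the baseline mismatch. With Day 1 differences and the re-dose score as covariate, signs are mixed in the main cases, and all four are negative in Model B's low-noise case.
- **The durability statement is not about these columns.** This stands. A reader might infer that the SAP rests its durability claim on the timing split. The sentence sits under the pooled Weeks 4-12 comparison, which is the sound one.
- **The bias is small per week.** Model A gives -0.27/8 = -0.03, 0.68/12 = +0.06, 1.16/16 = +0.07 and 1.48/20 = +0.07 points; Model B gives up to 3.22/20 = +0.16. This is fair, and most simulated columns are not falsely significant. The test is still well above its nominal 5%.
- **Re-dosing is not purely score-driven.** Benefit, clinical indication and a clinical rationale also count. These weaken the effect without removing it, so regression to the mean cannot be called the whole of any observed difference.
- **Efficacy is exploratory and safety is primary.** True. It limits the importance of the point but does not make these p-values interpretable.

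**Conclusion.** The point holds in a bounded form. The by-timing columns condition on first-dose outcomes under any baseline. With Day 1 baseline and equal doses, dose 2 appears better by about 0.3 score-weeks in the Week 12 column and worse by about 0.7 to 1.6 in the later ones. False significance is roughly 15-25% per column in one model and up to 43% in the other. The direction held in every score-driven scenario with within-patient variation; the sizes rest on assumed SDs and curves.

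A reader might go further and reject every within-patient AUE comparison. That is not supported. The pooled comparison to re-dosing is only mildly biased, because column biases partly cancel. The pooled Weeks 4-12 comparison is essentially unbiased in the main cases, provided that Day 1 is the baseline for both doses and the re-dose score is not a covariate. The SAP does not yet settle that condition. WOMAC B, C and total were not simulated and would be affected only as far as they track WOMAC A. The change is worth making, though the primary objective does not depend on it.

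**What to change.** 1. In SAP 4.9.1.4, reconcile the rule under the AUE formula with the later baseline statements. Name one inferential AUE comparison: Weeks 4-12 after each dose, all two-dose patients pooled, Day 1 baseline for both doses' differences, and no re-dose-visit score as covariate. Site and Day 1 score may stay.
2. Keep the CI and p-value for that comparison only.
3. Show the four timing columns, and the whole comparison from Week 4 to the second dose, as descriptive means without CI or p-value. Add a footnote that column membership and window end depend partly on the patient's own WOMAC A score.

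**Cost:** SAP wording and table shells, and the loss of some exploratory p-values. No data are lost, and the analysis to which the durability statement refers is kept.

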##### Comparison of change from baseline to Week 12 for the first and second doses

AUE for WOMAC A, WOMAC B, WOMAC C and WOMAC total change from baseline for the first dose from Week 4 Week 12 will be compared to AUE for WOMAC A, WOMAC B, WOMAC C and WOMAC total for the change from baseline for the second dose from 4 to 12 weeks after the second dose using a paired t-test. The examination of WOMAC A (Pain) will be an indication of the durability of the pain relief response, where WOMAC B (Stiffness) and WOMAC C (Function) will provide an indication of the durability of the responses for these two sub-scales over the course of two doses.

The paired t-test will be completed by using the SAS/STAT® PROC MIXED procedure. Model covariates are study site, baseline WOMAC score, and potentially other covariates. Baseline WOMAC score for the first dose comes from the first dose visit. Baseline WOMAC score for the second dose comes from the second dose visit. Sample SAS code provided in section 4.9.1.2 will be used.

Descriptive statistics will include the LSM and standard error, 95% confidence interval, LSM difference from control (first dose Week 4 to Week 12), and 2-sided p-value. This model assumes missing at random and only includes observed data; missing data are not imputed in

this model. Only patients that have data for both time points (i.e., first dose Week 4 to Week 12 and second dose Week 4 to Week 12) will be included in the model.

All patients who receive two doses of FX006 will be combined in the analysis and results will be displayed in the same column.

The analysis above will also be performed where baseline for the second dose is defined as the baseline/Day 1 assessment prior to administration of the first dose of study treatment.

Comparison of change from baseline to second dose and change from second dose to comparable period after second dose

AUE for WOMAC A, WOMAC B, WOMAC C and WOMAC total change from baseline for the first dose from Week 4 to the second dose will be compared to the AUE for WOMAC A, WOMAC B, WOMAC C and WOMAC total change from baseline for the second dose from 4 weeks after the second dose to the comparable period after the second dose using a paired t-test.

The paired t-test will be completed by using the SAS/STAT® PROC MIXED procedure. Model covariates are study site, baseline WOMAC score, and potentially other covariates. Baseline WOMAC score for the first dose comes from the baseline visit. Baseline WOMAC score for the second dose comes from the second dose visit. Sample SAS code provided in section 4.9.1.2 will be used.

Descriptive statistics will include the LSM and standard error, 95% confidence interval, LSM difference from control (first dose to second dose), and 2-sided p-value. This model assumes missing at random and only includes observed data; missing data are not imputed in this model. Only patients that have data for both time points will be included in the model.

Table 3 shows the AUE intervals that will be computed and compared:

**Table 3 AUE Change from Baseline Comparisons**

AUE	Patients receiving the second dose at Week 12	Patients receiving the second dose at Week 16	Patients receiving the second dose at Week 20	Patients receiving the second dose at Week 24
First Dose	Week 4 to Week 12	Week 4 to Week 16	Week 4 to Week 20	Week 4 to Week 24
Second Dose	Second Dose Week 4 to Week 12 (Week 16 to Week 24)	Second Dose Week 4 to Week 16 (Week 20 to Week 32)	Second Dose Week 4 to Week 20 (Week 24 to Week 40)	Second Dose Week 4 to Week 24 (Week 28 to Week 48)

Both within patient analyses will be presented in the same table. Each group will be displayed as a different column in the same table, in this order:

1. All patients receiving two doses
2. Patients receiving the second dose at Week 12

3. Patients receiving the second dose at Week 16
4. Patients receiving the second dose at Week 20
5. Patients receiving the second dose at Week 24

The analysis above will also be performed where baseline for the second dose is defined as the baseline/Day 1 assessment prior to administration of the first dose of study treatment.

All AUE data will be presented in a data listing. For patients receiving only one dose, the AUE for change from baseline for Week 4 to Week 12 will be presented.

#### **4.9.2. KOOS**

The KOOS QOL subscale (<http://www.koos.nu/>) has 4 questions, each of which is assigned a score from 0 to 4 (0=none, 1=mild, 2=moderate, 3=severe, 4=extreme). A normalized score (100 indicating no symptoms and 0 indicating extreme symptoms) is calculated using this formula:  $100 - \text{AVERAGE}(Q1-Q4)/4 * 100$ . Scores are calculated at each assessment time point (baseline, Week 4, Week 8, Week 12, etc.). Missing data rules are as presented in section 4.2.8.

The KOOS QOL subscale will be analyzed similarly to the WOMAC endpoints described in sections 4.9.1.1 and 4.9.1.2. Change from baseline calculations will be based on the same time points that are described for WOMAC.

#### **4.9.3. Daily activity measured as steps per day**

Steps per day data are collected from baseline to Week 12, so analysis only applies to a single injection of FX006. Weekly mean steps per day from Fitbit data will be calculated for baseline through Week 12 using the visit windows presented in section 4.2.9. Values of <1000 will be set to missing since they were considered invalid upon review of the data. Handling of missing data is presented in section 4.2.8.

A cumulative activity score will be calculated for each patient, defined as the incremental sum of the weekly average between Weeks 1 and 12. Incremental sum of weekly mean steps per day will be calculated as follows:

- Incremental sum (Week 1) = Weekly mean steps per day (Week 1)
- Incremental sum (Week 2) = Incremental sum (Week 1) + Weekly mean steps per day (Week 2)
- Incremental sum (Week x) = Incremental sum (x-1) + Weekly mean steps per day (Week x)

Descriptive statistics will include number of observations, unadjusted mean, standard deviation, median, minimum and maximum values by week. Values presented will be actual weekly mean steps per day, change from baseline in weekly mean steps per day, and incremental sum of weekly mean steps per day. A line plot will present each of these values by week.

A responder analysis will be performed in the same way that is described in section 4.9.1.3. Steps per day (Fitbit) responders are defined as patients who have  $\geq 10\%$  increase in weekly mean steps per day from baseline at a given visit.

The correlation between change from baseline in steps per day and change from baseline in WOMAC A, B, C and total score and the KOOS QOL subscale at Week 4, Week 8 and Week 12 will be explored. Pearson correlation will be used if both parameters are normally distributed. Spearman correlation will be used if either parameter is not normally distributed. The mean and median values for each parameter and the correlation coefficient will be presented in a table. Change from baseline for WOMAC A, B, C and total score and the KOOS QOL subscale versus change from baseline for average steps per day at Week 4, Week 8 and Week 12 will be presented in scatter plots, which will also include a best fit line.

A data listing will present steps per day for each patient as well as number of days that contributed to each weekly average and the number that were missing.

